2. OBJECTIVES AND ENDPOINTS

Objectives	Endpoints
Primary	
To compare gingivitis, as measured by BI, following twice daily use of an experimental 0.454% w/w stannous fluoride dentifrice compared to a fluoride control dentifrice after 12 weeks twice daily use.	Mean BI at 12 weeks.
Secondary	
To compare gingivitis, as measured by the number of bleeding sites using BI, following twice daily use of an experimental 0.454% w/w stannous fluoride dentifrice compared to a fluoride control dentifrice after 12 weeks twice daily use.	Number of bleeding sites at 12 weeks.
To compare gingivitis, as measured by MGI, following twice daily use of an experimental 0.454% w/w stannous fluoride dentifrice compared to a fluoride control dentifrice after 12 weeks twice daily use.	Mean MGI at 12 weeks.
To compare dental plaque scores (PI; overall and interproximal) following twice daily use of an experimental 0.454% w/w stannous fluoride dentifrice to a fluoride control dentifrice after 12 weeks twice daily use.	Mean PI (overall and interproximal) at 12 weeks.
Other	
To compare gingivitis, as measured by BI, following twice daily use of an experimental 0.454% w/w stannous fluoride dentifrice compared to a fluoride control dentifrice after 6 weeks twice daily use.	Mean BI at 6 weeks.
To compare gingivitis, as measured by the number of bleeding sites using BI, following twice daily use of an experimental 0.454% w/w stannous fluoride dentifrice compared to a fluoride control dentifrice after 6 weeks twice daily use.	Number of bleeding sites at 6 weeks.
To compare gingivitis, as measured by MGI, following twice daily use of an experimental 0.454% w/w stannous fluoride dentifrice compared to a fluoride control dentifrice after	Mean MGI at 6 weeks.

Document Name	207014 protocol		
Type	Version	Document Identifier	Effective Date
eldo_clinical_doc	5.0; Most-Recent; Effective; CURRENT	090032d580d1fee8	05-Apr-2017 13:38:03
Reason For Issue			Auto Issue

6 weeks twice daily use.	
To compare dental plaque scores (PI; overall and interproximal) following twice daily use of an experimental 0.454% w/w stannous fluoride dentifrice to a fluoride control dentifrice after 6 weeks twice daily use.	Mean PI (overall and interproximal) at 6 weeks.
To evaluate and compare MGI and BI in low (≤ 2.00) and high (> 2.00) MGI subgroups following twice daily use of an experimental 0.454% w/w stannous fluoride dentifrice after 6 and 12 weeks twice daily use.	Mean MGI & BI at 6 & 12 weeks (in subgroups).
To evaluate examiner MGI & PI measurement reproducibility for a random subset of the study population.	Kappa coefficient for MGI & PI

Document Name	207014 protocol	Document Identifier	
Type	Version	Effective Date	
eldo_clinical_doc	5.0; Most-Recent; Effective; CURRENT	090032d580d1fee8	05-Apr-2017 13:38:03

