After using the study dentifrice twice daily for one timed minute at home for 6 and 12 weeks, subjects will return to the study site (Visits 3 and 4, respectively) having abstained from oral hygiene for 12hrs (+6hr, -2hr) i.e. from overnight immediately before each assessment visit, if possible at approximately the same time of day as the baseline visit. The study dentifrice will be collected and the diary reviewed for treatment compliance. Pregnancy testing will be carried out on all female subjects of child bearing potential at each visit. Subjects will have a full OST examination and then undergo, in the following order, MGI, BI followed by PI assessments after disclosing. At Visit 3, subjects will receive another supply of assigned study toothpaste, a new toothbrush and diary. At Visit 4, subjects will return all study materials and have a dental prophylaxis if deemed appropriate by the investigator or examiner.

At Visits 2, 3, 4, repeatability data will be generated for MGI & PI assessments from replicate examinations on the same subject. Depending on subject visit scheduling, every effort will be made to complete one repeatability examination for each clinical measure during each clinical session, that is, one in the morning and one in the

Document Name	207014 protocol	Document Identifier	Effective Date
Type	Version		
eldo_clinical_doc	5.0; Most-Recent; Effective; CURRENT	090032d580d1fee8	05-Apr-2017 13:38:03

afternoon on each assessment day. Repeatability examinations will be separated by a minimum of 10 minutes and, where possible, separated by another subject. Replicate BI examinations will not be performed.

Visit 1 - Screening Visit

The following assessments will be conducted:

- Informed consent
- Demographics, medical history, current / concomitant medication, & smoking status.
- Urine pregnancy testing will be carried out on all female subjects of child bearing potential.
- Oral soft & hard tissue (OST/OHT)examination
- Gross gingival assessment
- Inclusion/exclusion criteria
- Subject eligibility / continuance
- Subjects will be instructed to brush using their normal toothpaste and following their normal routine between screening and baseline visits.

Visit 2 - Baseline Visit; Day 0

The following assessments will be conducted:

- Review of current/concomitant medications, adverse events
- Urine pregnancy testing will be carried out on all female subjects of child bearing potential.
- Full OST examination
- MGI
- BI

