9.2. General Considerations

9.2.1. Definition of Analysis Populations

The intent to treat (ITT) population is defined as those subjects who are randomized, receive at least one dose of study product and have at least one post-baseline efficacy measurement.

The Per Protocol (PP) population will be a subset of the ITT population. Subjects with a protocol violation that is deemed to affect efficacy for all efficacy assessments will be excluded from the PP population. Subjects with a protocol violation that is deemed to affect efficacy for only some (but not all) of the efficacy assessments will be part of the PP population, but their data will be excluded from the assessment at which the protocol violation occurred. Efficacy analysis will be based on ITT population. A PP analysis will be performed only if 10% or more ITT subjects are excluded from PP population

Safety population is defined as all subjects who are randomized and have received at least one dose of study products.

The repeatability population is defined as all subjects who have a repeat clinical assessment (MGI or PI) at any visit.

Document Name	207014 protocol	Document Identifier	Effective Date
Type	Version		
eldo_clinical_doc	5.0; Most-Recent; Effective; CURRENT	090032d580d1fee8	05-Apr-2017 13:38:03

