9.3.5. Repeatability Analysis

A number of subjects will have repeat gingivitis (MGI and TPI) assessments conducted by the examiner. The repeat assessments will be compared to the original assessments. The repeat assessments will not be used in any efficacy analysis. The purpose of repeated assessments is to check the consistency of the examiner. As each subject will provide around 100 records for repeatability judgement, one subject on the morning and one subject in the afternoon in each visit day over the course of the study is sufficient for repeatability assessment. The first and second assessments on each tooth at a given visit will be cross-tabulated and a weighted Kappa coefficient (κ) will be calculated, along with the 95% confidence interval, to assess the intra-examiner repeatability. Repeatability will be deemed [Fleiss]:

- Excellent, if $\kappa > 0.75$
- Fair to good, if $0.4 \leq \kappa \geq 0.75$
- Poor if $\kappa < 0.4$

All subjects who have repeatability data will be included in this analysis.

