4.1.3 Analysis Populations

Six analysis populations are defined.

Population	Definition / Criteria	Analyzes Evaluated
All Screened Subjects	All subjects who are screened	Disposition
Randomized	All subjects who are randomized and may or may not receive the application of the study products.	Protocol deviations
Safety	Safety population includes all subjects who are randomized, administered a study product at least once.	Safety analysis
Intent-to-Treat (ITT)	The ‘Intent to treat’ (ITT) population includes all subjects who are randomized, administered the study product at least once and provide at least one post-baseline assessment of efficacy.	Efficacy analysis
Per-Protocol (PP)	The Per Protocol (PP) population is a subset of the ITT population which excludes subjects with a protocol violation that is deemed to affect efficacy for all efficacy	Efficacy analyzes for BI score and number of bleeding sites and MGI score.

Population	Definition / Criteria	Analyzes Evaluated
	assessments. Subjects with a protocol violation that is deemed to affect efficacy for only some (but not all) of the efficacy assessments will be part of the PP population. PP analyzes will use only the data considered unaffected by protocol violations.	
Repeatability population for modified gingival index (MGI) assessment	All subjects who have an initial and a repeat assessment on MGI.	Repeatability analysis
Repeatability population for plaque index (PI) assessment	All subjects who have an initial and a repeat assessment on PI.	Repeatability analysis

The primary population for assessment of efficacy will be the ITT population. A PP analysis will be performed on the primary variable only if more than 10% of the subjects in the ITT population are excluded from the PP population.

The numbers of subjects excluded from each population broken down by the reason for exclusion will be presented ([Table 14.1.2](#)). Subjects excluded from any of the analysis populations will be listed ([Listing 16.2.3.1](#)).

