4.8 Analysis of Other Variables

A number of subjects will have repeated plaque index (PI) or gingivitis index (MGI) assessments conducted by the examiner. The repeat assessments will be compared to the original assessments separately for PI and MGI. The repeat assessments will not be used in any efficacy analysis. The first and second assessments on each tooth at a given visit will be cross-tabulated and a weighted Kappa coefficient (κ) will be calculated, along with the 95% confidence interval, to assess the intra-examiner repeatability ([Table 14.2.6](#) and [Table 14.2.7](#)). Repeatability will be deemed

- Excellent, if $\kappa > 0.75$
- Fair to good, if $0.4 \leq \kappa \leq 0.75$
- Poor if $\kappa < 0.4$

All subjects who have repeatability data will be included in this analysis. SAS PROC FREQ will be used for this analysis with codes similar to the following:

GlaxoSmithKline Consumer Healthcare Confidential

```
PROC FREQ DATA = INTRA;  
TABLES R1*R2/AGREE (wt = fc);  
RUN;
```

Where R1 = first assessment score by an assessor, R2 = second (repeat) assessment score by an assessor.

5 Changes to the Protocol Defined Statistical Analysis Plan

There is no change to the planned statistical analysis specified in the protocol version 5.0 [(Dated: 05/Apr/2017)].

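### The reproducibility objective promises a random subset, but neither document provides a random selection of repeat subjects or conceals the choice from the examiner

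*Protocol*

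**What the plan says.** Three objective tables carry the same aim: the protocol synopsis, protocol section 2 and SAP section 1.2. The wording is "To evaluate examiner MGI & PI measurement reproducibility for a random subset of the study population", with kappa for MGI and PI as the endpoint.

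The working rule is in protocol section 3.1: "Depending on subject visit scheduling, every effort will be made to complete one repeatability examination for each clinical measure during each clinical session". The synopsis and section 3.4 say the same, and sections 6.2.3 (MGI) and 6.2.5 (PI) repeat it in shorter form. Section 9.3.5 does not mention scheduling. It gives the number, stating that "one subject on the morning and one subject in the afternoon in each visit day over the course of the study is sufficient" for the purpose.

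The populations are defined by outcome, not by selection. Protocol 9.2.1 says "The repeatability population is defined as all subjects who have a repeat clinical assessment (MGI or PI) at any visit". SAP 4.1.3 says "All subjects who have an initial and a repeat assessment on MGI", with a matching definition for PI. SAP 4.8 says only that "A number of subjects will have repeated plaque index (PI) or gingivitis index (MGI) assessments conducted by the examiner".

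The only randomization schedule described (protocol 5.8 and 5.8.1) assigns study product. Examiner blinding (5.8.2) covers treatment received and nothing else.

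**The concern.** An objective stated for a random subset needs a procedure that produces one, and none is given. Scheduling decides whether a repeat can be fitted into a session. The documents do not say who picks the subject, on what basis, or when the examiner learns of it.

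Two things follow. The repeat subjects may differ from the study population in how easy they are to grade or in how varied their scores are, and weighted kappa is sensitive to both. An examiner who knows that a mouth will be re-scored may also grade it differently the first time.

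The stake is modest but real. Each index is scored by one examiner throughout, and BI is not replicated (6.2.4). The MGI and PI kappas are therefore the only replicate-based check on scoring consistency in the plan. They are read against fixed cut-offs, so a shift near 0.4 or 0.75 would change the reported label.

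**Working it through.** **1. The plan's own figure.** Section 9.3.5 supports its sample with a record count: "As each subject will provide around 100 records for repeatability judgement". Inputs: at least 20 teeth (4.1, criterion 5a); at most 28, since teeth 7-7 in each arch are scored; 4 MGI scores per tooth (6.2.3); 6 PI scores per tooth (6.2.5).

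- MGI: 4 × 20 = 80 to 4 × 28 = 112 records. This brackets 100.
- PI: 6 × 20 = 120 to 6 × 28 = 168 records. All above 100.

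The figure is approximate and fits MGI. It counts records within a mouth and says nothing about which mouths are taken. The number of visit days is not given, so the number of repeat subjects cannot be computed.

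**2. Objective against procedure.**

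| Element | Where | Random selection? |
|---|---|---|
| Objective | Synopsis, protocol 2, SAP 1.2 | Promised |
| Working rule | Synopsis, 3.1, 3.4, 6.2.3, 6.2.5 | Not stated; best effort, subject to scheduling |
| Number per day | 9.3.5 | Not stated |
| Analysis population | 9.2.1, SAP 4.1.3 | Not stated; whoever has a repeat |
| Analysis | 9.3.5, SAP 4.8 | Not stated |
| Concealment from the examiner | 5.8.2 | Treatment only |

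**3. Can selection move kappa, and which way?** The documents give no inputs for this, so an illustrative MGI simulation was run.

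- From the documents: 120 subjects, subject means within the baseline eligibility band 1.75-2.30, and the Fleiss-Cohen weights in the SAP 4.8 code.
- Assumed: subject means uniform over that band, 96 sites per mouth (24 teeth × 4), within-mouth SD 0.4-0.9, grading-error SD 0.3-0.7, 30 repeat subjects, 400 replicates. Non-random subsets were drawn from one half of the subjects, ranked on the feature named.

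| How the repeat subjects were taken | Mean kappa | Against all subjects |
|---|---|---|
| All subjects | 0.57 | – |
| Random subset | 0.57 | 0 |
| By schedule, unrelated to scores | 0.57 | 0 |
| Easier to grade | 0.65 | +0.08 |
| Harder to grade | 0.50 | −0.07 |
| More varied mouths | 0.64 | +0.07 |
| More uniform mouths | 0.47 | −0.10 |

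Selection matters only if it is related to gradability or score spread, and it can then act in either direction. In this example every value stays between 0.4 and 0.75, so no label changes. A label would change only if the true kappa lay close to a cut-off.

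**4. Selection chances.** One repeat in a session of n subjects, drawn at random, gives each a chance of 1/n. Session sizes are not in the documents. For illustration, n = 2 gives 1/2 and n = 12 gives 1/12. A random draw within the session makes the chances known but not equal.

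**The case against.** The scheduling clause governs whether a repeat is achieved, not who is taken. The choice within a session is open and so compatible with the random draw that the objective promises. This stands. A reader might infer that the rule itself produces a convenience sample of whoever is willing to wait. The documents do not say so; they support only the statement that random selection is not specified.

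A reader might also infer that the kappas will be optimistic. The documents give no direction, and step 3 shows that bias could be upward, downward or absent. Nor can a shift be sized: session sizes, the spread of kappa between mouths and any link between selection and ease of grading are all missing.

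Examiner foreknowledge would arise with a random subset too, so it is not evidence of the mismatch. That is correct, but it is a gap in the same procedure and the same list closes it. Recall between examinations is a separate matter and is partly addressed: "Repeatability examinations will be separated by a minimum of 10 minutes and, where possible, separated by another subject".

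Finally, the consequences are limited. This is one of the objectives listed as other; both documents keep repeat scores out of every efficacy analysis; the success criterion (9.2.4) rests on BI alone; and the output is titled for the repeatability population. All of this stands and sets the weight of the point. It does not reconcile the objective with the procedure.

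**Conclusion.** The point holds as a mismatch between objective and method. All three objective tables promise a random subset, no section provides random selection, and nothing keeps the examiner from choosing the repeat subject or knowing of the repeat during the first scoring. The MGI and PI kappas may therefore not represent the study population.

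The direction and size of any bias cannot be derived from the documents. The differences of −0.10 to +0.08 in the simulation rest on assumed inputs and on selecting from one half of the subjects. They also use the baseline MGI band, although repeats are taken at Visits 3 and 4 as well. They show that selection can matter, not that it did. Efficacy conclusions are untouched. This is a low-cost improvement, not a threat to the trial.

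**What to change.** State a selection rule in the protocol synopsis and in sections 3.1, 3.4, 6.2.3 and 6.2.5, where the scheduling wording now stands. Add it to protocol 9.3.5 and SAP 4.8, which have no selection wording to replace. The rule should say that:

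- for each session, a pre-generated random list names the appointment slot to be repeated, with the next slot as backup;
- site staff other than the examiner hold the list;
- the examiner is told only after that subject's first MGI (or PI) scores have been recorded;
- the session size is recorded, because selection chances are known but not equal.

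The cost is one short list and a few sentences. The number of repeat examinations does not change. The downside is that an occasional subject has to wait, or the backup slot is used.

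If the scheduling rule is kept, or the repeats have already been done, delete the word random from all three objective tables (protocol synopsis, protocol section 2, SAP 1.2) and report how the repeat subjects were chosen.

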3. STUDY PLAN

3.1. Study Design

Overall Design

This will be a single-centre, examiner-blind, randomized, stratified, two-treatment, parallel group, clinical study in healthy adult volunteers with moderate gingivitis. There will be four visits to the study site: Screening, Baseline, 6 Week and 12 Week. Gingivitis will be assessed using a Modified Gingival Index (MGI; Lobene, 1986) and a Bleeding Index (BI; Saxton, 1989). Plaque will be assessed by the Turesky modification of the Quigley & Hein Plaque Index (PI; Lobene, 1982).

At the Screening visit (Visit 1), subjects will give their written informed consent to participate in the study. Demographics, medical history, current and concomitant medications will be recorded, followed by an oral examination and a gingival assessment. Pregnancy testing will be carried out on all female subjects of child bearing potential at each visit. This will include full oral soft tissue (OST) and oral hard tissue (OHT) examinations, including dentition exclusions and gingival status. Subjects will be instructed to brush using their normal toothpaste and following their normal routine between screening and baseline.

Within 1-28 days of Screening (Visit 1), eligible subjects will return to the site for the Baseline visit (Visit 2) with overnight plaque (subjects will abstain from oral hygiene for 12hrs (+6hr, -2hr) i.e. overnight immediately before the visit). At the Baseline visit, subjects will undergo, in the following order, a full OST examination and assessments of gingival inflammation (MGI followed by BI), and supra- gingival plaque (PI).

Subjects with a suitable number of gradable teeth, with a mean overall MGI score between 1.75-2.30 and mean overall PI score ≥ 1.5 will continue in the study. Subjects with a mean overall MGI or PI scores outside the study range will be discontinued from the study at this visit. To control inter-examiner variability, the same suitably qualified examiner will be used throughout the study for each of the measures. The same examiner can perform more than one assessment but the same examiner must perform each of these assessments for all subjects throughout the study.

Subjects will be instructed to abstain from toothbrushing for a minimum of 12hrs (+6hr, -2hr) i.e. overnight immediately before each assessment visit. At the Baseline visit subjects will undergo a baseline oral soft tissue (OST) assessment, MGI

Document Name	207014 protocol	Document Identifier	Effective Date
Type	Version		
eldo_clinical_doc	5.0; Most-Recent; Effective; CURRENT	090032d580d1fee8	05-Apr-2017 13:38:03

followed by a BI followed by dental plaque (PI) assessment (assessments must occur in the order written) for all teeth meeting the inclusion criteria. Following the MGI & BI assessments, and after rinsing with 20ml of water, subjects will rinse their mouth with disclosing solution before receiving a dental plaque assessment.

Eligible subjects will be stratified based on gender (male/ female), smoking status (yes/ no) and baseline mean overall MGI score (low: ≤ 2.00 ; high > 2.00) to ensure a balance in treatments across the strata, and then randomized into one of two treatment groups. Dental prophylaxis will be performed by a suitably qualified member of site staff for each subject using a standard dental prophylaxis paste followed by flossing by the examiner. Subject's teeth will be disclosed using a disclosing solution to check for residual plaque. A second clinician will check to ensure all plaque has been removed. Any residual plaque & calculus remaining will be removed by the second clinician by dental polishing with a standard dental prophylaxis paste, to bring the subject to a confirmed score of zero visible plaque (PI=0).

Following dental prophylaxis, subjects will receive their assigned study dentifrice, a diary, a toothbrush, a timer and instructions on product usage and diary completion. Subjects will brush their teeth with their allocated dentifrice, in their usual manner for one timed minute, under supervision. Subjects will continue to brush twice daily (morning and evening) for one timed minute recording each brushing on their study diary.

After using the study dentifrice twice daily for one timed minute at home for 6 and 12 weeks, subjects will return to the study site (Visits 3 and 4, respectively) having abstained from oral hygiene for 12hrs (+6hr, -2hr) i.e. from overnight immediately before each assessment visit, if possible at approximately the same time of day as the baseline visit. The study dentifrice will be collected and the diary reviewed for treatment compliance. Pregnancy testing will be carried out on all female subjects of child bearing potential at each visit. Subjects will have a full OST examination and then undergo, in the following order, MGI, BI followed by PI assessments after disclosing. At Visit 3, subjects will receive another supply of assigned study toothpaste, a new toothbrush and diary. At Visit 4, subjects will return all study materials and have a dental prophylaxis if deemed appropriate by the investigator or examiner.

At Visits 2, 3, 4, repeatability data will be generated for MGI & PI assessments from replicate examinations on the same subject. Depending on subject visit scheduling, every effort will be made to complete one repeatability examination for each clinical measure during each clinical session, that is, one in the morning and one in the

Document Name	207014 protocol	Document Identifier	Effective Date
Type	Version		
eldo_clinical_doc	5.0; Most-Recent; Effective; CURRENT	090032d580d1fee8	05-Apr-2017 13:38:03

afternoon on each assessment day. Repeatability examinations will be separated by a minimum of 10 minutes and, where possible, separated by another subject. Replicate BI examinations will not be performed.

Visit 1 - Screening Visit

The following assessments will be conducted:

- Informed consent
- Demographics, medical history, current / concomitant medication, & smoking status.
- Urine pregnancy testing will be carried out on all female subjects of child bearing potential.
- Oral soft & hard tissue (OST/OHT)examination
- Gross gingival assessment
- Inclusion/exclusion criteria
- Subject eligibility / continuance
- Subjects will be instructed to brush using their normal toothpaste and following their normal routine between screening and baseline visits.

Visit 2 - Baseline Visit; Day 0

The following assessments will be conducted:

- Review of current/concomitant medications, adverse events
- Urine pregnancy testing will be carried out on all female subjects of child bearing potential.
- Full OST examination
- MGI
- BI
- PI (following plaque disclosure)
- Inclusion/exclusion criteria
- Subject eligibility / continuance
- Stratification/randomization
- Sub- & supra-gingival prophylaxis & flossing (with second clinician check after disclosing & residual plaque removal, if applicable)
- Confirmed plaque score of 0 following dental prophylaxis.
- Dispense study dentifrice, toothbrush, study instructions, diary & timer
- Oral hygiene instruction review / compliance checks including diary completion review with subject
- Supervised subject brushing at site
- Adverse events

Visit 3 - Week 6; Day 42+/-3

The following assessments will be conducted:

Document Name	207014 protocol		
Type	Version	Document Identifier	Effective Date
eldo_clinical_doc	5.0; Most-Recent; Effective; CURRENT	090032d580d1fee8	05-Apr-2017 13:38:03
Reason For Issue	Auto Issue		

- Review of current/concomitant medications, adverse events
- Compliance checks including diary review
- Urine pregnancy testing will be carried out on all female subjects of child bearing potential.
- Subject eligibility / continuance
- Full OST examination
- MGI
- BI
- PI (following plaque disclosure)
- Collect study dentifrice, toothbrush & diary
- Dispense study dentifrice, toothbrush, study instructions, diary & timer
- Oral hygiene instruction review / compliance checks including diary completion review with subject
- Supervised subject brushing at site
- Adverse events

Visit 4 - Week 12; Day 84+/-3

The following assessments will be conducted:

- Review of current/concomitant medications, adverse events
- Compliance checks including diary review
- Urine pregnancy testing will be carried out on all female subjects of child bearing potential.
- Subject eligibility / continuance
- Full OST examination
- MGI
- BI
- PI (following plaque disclosure)
- Collect study dentifrice, toothbrush & diary
- Oral hygiene instruction review / compliance checks including diary completion review with subject
- Complete optional second dental prophylaxis (as/ if deemed necessary by examiner)
- Adverse events
- Study conclusion

